#### D. Power Analysis

Our power calculation is based on the Aim 1A outcome of cotinine-verified smoking abstinence at 12 weeks. With a sample arm of 90 per arm, we will have >80% power to detect a difference in abstinence at 12 weeks of 4% in the control arm and 17.5% in the incentives arm at a two-tailed p of 0.05.

## **VII. RISKS AND DISCOMFORTS**

The potential risks and discomforts associated with this study are detailed below. The methods for mitigating these risks and monitoring the safety of participants are described in section IX.B.

#### A. Complications of surgical/non-surgical procedures

Not applicable.

#### B. Drug side effects and toxicities

Participants will be offered a prescription for varenicline. Common side effects of varenicline are nausea, sleep problems, constipation, gas, and vomiting. Other possible, but less common, side effects include cardiovascular (chest pain, hypertension, tachycardia), sleep walking, allergic reactions, or serious skin reactions. Participants who are taking varenicline prescribed by the study clinician will be assessed for varenicline side effects and suicidality at each on-treatment monitoring visit. Procedures for addressing participants with significant side effects and suicidality are described below (section IX. D.).

In June 2021, Pfizer announced a halt in global distribution of varenicline (brand name: Chantix) and a voluntary recall of selected lots after finding heightened levels of N-nitroso-varenicline (a nitrosamine compound) in some pills. Although the risk posed by N-nitroso-varenicline is uncertain, nitrosamine compounds in general are considered carcinogenic when exposure occurs in sufficient doses over prolonged periods of time. The nitrosamine levels found in Pfizer's varenicline product exceeded the FDA's acceptable intake limit of 37 ng per day. In September 2021, Pfizer extended its recall to all lots of varenicline.

The FDA has since approved two generic versions of varenicline: one manufactured by Apotex and one manufactured by Par Pharmaceuticals. The FDA also announced that they would not object to manufacturers distributing varenicline tablets above the FDA's original acceptable intake limit of 37 ng per day but below an interim acceptable intake limit of 185 ng per day. Both of the above generic versions of varenicline distributed by Apotex and Par have levels of N-nitroso-varenicline that are within the FDA's interim acceptable intake limit.

Study staff are working closely with the BHCHP pharmacy to ensure participants receive a varenicline product that falls within these interim safe limits. During informed consent, staff will inform participants of the risk of contamination of varenicline products while also clarifying that the versions they will receive have been deemed safe by the FDA.

#### C. Device complications

Not applicable.

#### D. Psychosocial (non-medical) risks

- i) Psychological and/or physical discomfort: Quitting smoking can be psychologically stressful and, at times, physically uncomfortable because of cravings and nicotine withdrawal symptoms, such as irritability, depressed mood, sleep difficulty, and concentration difficulty. Participants will be asked to what extent they have craved cigarettes at each on-treatment monitoring visit.
- ii) Risk to privacy: We will collect and record identifying information (e.g. name, date of birth, and social security number) and ask participants about potentially sensitive topics. There is a risk to privacy if this data is compromised.

#### E. Radiation risks

Not applicable.

#### G. Potential loss of study mobile phone

Participants may be at minimal risk of a breach of privacy if someone else gains access to their phone during the study. Therefore, we will inform participants of this risk during recruitment and encourage participants to mitigate this risk by 1) not sharing their phone with others, 2) password protecting their mobile device, and 3) in the event of loss, notifying research staff to terminate service to the device. Automated appointment reminder text messages will be sent to participants. These text messages are designed to convey relevant information to participants while having a protective level of ambiguity.

### **VIII. POTENTIAL BENEFITS**

#### A. Potential benefits to participating individuals

Potential benefits for participants include the opportunity to receive assistance with smoking cessation, which may reduce their risk of tobacco-related health complications in addition to reducing the amount of money they direct toward purchasing cigarettes. The scope and magnitude of these potential benefits outweigh the risks to human subjects.

#### B. Potential benefits to society

As in the general population, cigarette smoking is a major contributor to morbidity and mortality among homeless people. Strategies to reduce smoking among homeless people may reduce the personal and financial costs of smoking-related health complications in this population. Knowledge gained from this study could contribute to this effort by improving the treatment of homeless smokers in other settings.

### **IX. MONITORING AND QUALITY ASSURANCE**

We judge the proposed study to represent a low-risk phase III behavioral intervention trial. In view of the vulnerable nature of the study population, we will create a Data and Safety Monitoring Board (DSMB), consisting of researchers not involved in the study who have expertise in clinical trials and/or vulnerable populations, to oversee the integrity of the data and

the safety of participants. The objectives and procedures of the DSMB are explained further below (section IX.I.). The following data and safety monitoring procedures (sections IX.A.-IX.G.) will be implemented throughout the study.

#### A. Data acquisition and monitoring

All data will be collected using password-protected, Mass General Brigham-approved laptops or tablets with full-disk encryption. We will use the Mass General Brigham-hosted Research Electronic Data Capture (REDCap) application for data collection and management. REDCap is a secure, HIPAA-compliant web-based application hosted by Mass General Brigham HealthCare Research Computing Enterprise Research Infrastructure & Services (ERIS). Because a Mass General Brigham username is required for logging in to REDCap, all activity on study documents is electronically logged and therefore traceable. To help guard against errant data entries, REDCap has built-in functions providing real-time data entry validation to help ensure accuracy and completeness. Data will be collected according to a standardized protocol that will detail which data elements should be collected at each study visit and the methods for doing so. We will operationalize this protocol by using the calendar function in REDCap to specify which data collection forms to administer on which dates for each participant. Each data collection form will have instructions or prompts for collecting the required data elements, and the response fields for each item will have appropriate ranges and formats to ensure that the data is entered in a valid way.

Data collected in REDCap is saved by default to a secure, HIPAA-compliant server. To help ensure the safety and integrity of the study data, the data will be periodically exported from REDCap and backed up to a HIPAA-secure shared file area (SFA) accessible only to authorized study staff after logging on to the Mass General Brigham network. Data saved to the study SFA can be accessed only via the Mass General Brigham-approved computing device, which by default includes antivirus software and, if the device is portable, full-disk encryption. The SFA is backed up nightly by the Mass General Brigham Information Systems department to guard against data loss or corruption. Access to the study SFA will be overseen by the PI and can be changed only by a designated key-giver (who is independent of the study) under the explicit direction of the PI. In addition to the SFA, selected data elements may also be stored on a project-dedicated Mass General Brigham Microsoft SharePoint site. Data saved on the project-dedicated SharePoint site will be accessible only to study staff.

The qualitative interviews conducted at 12 and 24 weeks will be recorded by a microphone connected directly to a password-protected, Mass General Brigham-approved laptop or tablet with full-disk encryption. Audio files will be backed up to the PI's SFA described above and then deleted from the portal device.

The study data will be examined on a weekly basis by the REDCap database programmer, working in conjunction with the PI, to identify patterns of missing data or non-response, to ensure that critical variables are being captured and recorded as intended, and to generate recruitment and enrollment reports for review by the PI in conjunction with the co-investigators. Free-text notes recorded by data collectors will be examined to identify potentially problematic items that may require additional clarification. The database programmer will prepare cleaned, de-identified analytic datafiles for use by the biostatistician to conduct the data analyses described in the Research Strategy. Analyses will occur periodically throughout the study and

the findings will be reported in annual progress reports to the NIH and in continuing review reports for the Mass General Brigham IRB.

#### B. Quality assurance

The tobacco coach will complete a checklist indicating topics covered during the counseling sessions and will record process notes after each session. He/she will record experiences delivering the intervention including the ease of delivery (including the length, scheduled time); the apparent acceptability and relevance; comprehension of the material by the participants; and factors that impeded or assisted in the delivery, and any issues related to safety or potential harms that emerge.

Using a random selection process, the tobacco coach will identify a sub-sample of 15% of sessions to audio record. A clinical psychologist will periodically review the recordings and provide direct feedback to the tobacco coach using a standard coaching evaluation form rating adherence to the protocol, adherence to motivational interviewing principles, use of motivational interviewing tools/techniques, and participant engagement. The coach will obtain verbal consent from participants before starting the recording. Sessions will be recorded by a microphone connected directly to a password-protected, Mass General Brigham-approved laptop or tablet with full-disk encryption. Audio files will be backed up to the PI's SFA described above and deleted from the portable device. Audio files will also be destroyed immediately after review. The coaching evaluation forms will not contain any identifying information and will be securely stored on Microsoft Sharepoint.

#### C. Safety Monitoring

The eligibility criteria for the study are designed to identify individuals who would most likely benefit from the proposed intervention. These criteria represent an expansion of the criteria used in our pilot RCT, enabling the proposed intervention to reach a broader target population. Although all current smokers should be advised to stop smoking and offered assistance in quitting, we believe that the proposed financial incentives approach is best targeted to individuals who are least contemplative about quitting (i.e. planning to quit in the next 3 months). Whether financial incentives might motivate interest in smoking cessation among pre-contemplative smokers is a separate scientific question that merits separate investigation.

During eligibility screening, participants will be asked about potential contraindications to varenicline, including questions about suicidality via the primary care screening version of the C-SSRS (see Appendix 3). Individuals at low risk of suicide will be allowed to participate while being made aware of available behavioral health care resources, including 24-hour crisis line numbers and on-site mental health services at BHCHP. Individuals at moderate risk of suicide only due to history of suicidal behavior >12 months prior (and not due to current suicidal thoughts) will be allowed to participate if all other criteria are met, and will be made aware of available behavioral health care resources. Individuals at moderate risk of suicide due to history of suicidal behavior in the past 3-12 months (and not due to current suicidal thoughts) will be excluded and made aware of available behavioral health care resources. Individuals at moderate risk of suicide due to suicidal thoughts with methods but without intent will be excluded from the study, provided 24-hour crisis line numbers, and encouraged to make an appointment with a behavioral health clinician (at BHCHP or elsewhere) within 3 business days.

Individuals at high risk of suicide due to past 3-month suicidal behavior (with no current suicidal intent) will also be excluded from the study and encouraged to make an appointment with a behavioral health clinician within 3 business days. Individuals at high risk of suicide due to current suicidal intent based on the C-SSRS will be excluded from the study and referred immediately for an urgent on-site same-day mental health evaluation by BHCHP clinical staff.

To ensure that eligible participants have an adequate understanding of the potential risks associated with study participation, all participants will be informed of these risks in plain language on a written informed consent document that will be read aloud to each participant, making no assumption of literacy. Participants will be informed of the option of not participating in the study and that their decision regarding study participation will in no way impact their ability to receive future services at BHCHP. Following a practice we established in our prior survey work involving homeless smokers and further refined in our pilot RCT for homeless smokers, we will confirm individuals' understanding of the consent materials with basic knowledge questions about the consent document content to ensure that they have the capacity to provide informed consent. Individuals who can correctly answer these questions will be asked to sign the paper consent form if they wish to enroll in the trial. A signed copy will be retained by study staff and a second signed copy of the consent form will be given to participants for their own records.

During the trial, participants will be asked proactively about side effects at regular intervals during monitoring visits and encouraged to report side effects to varenicline at any time. Adverse reactions will be tracked and addressed according to the adverse event procedures outlined below. Participants will be asked to rate the severity of their side effects as none, mild, moderate, or severe. Mild reactions will be recorded and monitored, and participants will be encouraged to let study staff know if they worsen or persist. If a participant rates a side effect as moderate, study staff will ask if the participant wants to speak with a clinician. If so, the clinician will phone participants within 48 hours to assess their symptom(s) and formulate a plan, which could include continuing as is, modifying the dose of varenicline, or stopping varenicline. If a participant experiences severe side effects, study staff will advise the participant to immediately stop taking varenicline. The study clinician and PI will be notified and will follow-up with the participant within 24 hours to decide with the participant about whether to remain off varenicline or resume the medication at a lower dose. Severe, potentially life-threatening reactions (e.g., cardiac complications) will prompt immediate on-site medical assessment by a health care provider at BHCHP headquarters or at a nearby hospital. The study clinician and PI will be notified and will follow-up with the participant within 24 hours.

Study staff will also proactively assess suicidality at every on-treatment monitoring visit using a modified version of the C-SSRS (see Appendix 3). Participants at low risk for suicide based on the C-SSRS will be made aware of available behavioral health care resources, including crisis line numbers and on-site mental health services at BHCHP. Participants at moderate risk for suicide based on the C-SSRS will be given 24-hour crisis line numbers and encouraged to schedule a visit with their PCP or an on-site behavioral health provider within 2 business days, with assistance from study staff. The study clinician or PI will call these participants within 24 hours to discuss their suicidality and reinforce the above evaluation plan. Participants at high risk for suicide based on the C-SSRS will be escorted immediately to the on-site BHCHP clinic for an urgent mental health evaluation by BHCHP clinical staff. Study staff will advise these participants to stop varenicline. The study clinician and PI will be notified and will follow-up with

the participant within 24 hours to discuss the plan for moving forward. In instances in which participants show moderate or high risk of suicide based on the C-SSRS, study staff will communicate with participants' PCPs via secure Epic messaging regarding the outcome of this assessment within 2 business days (if moderate risk) or within 24 hours (if high risk). Although suicidality will not be proactively assessed during tobacco coaching sessions, if participants spontaneously bring up suicidal thoughts, the tobacco coach will follow similar procedures to the monitoring visits and assess suicidality risk using the modified C-SSRS and react accordingly based on level of risk.

If a participant misses their monitoring visit, this will trigger an automated text message to their study phone or personal phone advising them to call study staff if they are experiencing any side effects or other concerns related to their participation in the study (see Appendix 1).

If a participant calls study staff with concerns, study staff will make a note of any reported side effects and their severity in a manner similar to that which would occur during an in-person monitoring visit. However, to improve the efficiency of phone encounters, reduce the use of participants' cell phone minutes and allow the participant to direct the conversation in a more fluid way, a complete checklist of side effects and the C-SSRS scale will not be administered by default during these phone calls unless dictated by participants' reported symptoms. If a participant reports mental health concerns, this will prompt administration of the (C-SSRS) over the phone, with triage according to the algorithm outlined for in-person monitoring visits.

Psychological status (including depression and anxiety symptoms) will be formally assessed at baseline, and at 12 and 24 weeks, providing additional opportunities to identify and address any psychological discomforts that participants may be experiencing. If any participant screens positive for any mental health disorders listed, study staff will ask participants whether they are currently receiving behavioral health care and assist them with connecting or reconnecting with such care, either at BHCHP or at an outside facility (if preferred by the participant).

Study staff will be trained to recognize the signs of an intoxicated participant and to activate a response plan appropriate to the level of symptoms or impairment. Participants demonstrating evidence of mild substance intoxication will be informed of on-site behavioral health services to address substance use. Participants with more profound levels of intoxication causing substantial impairment in functioning and well-being will be referred for immediate on-site medical evaluation. The clinic at BHCHP headquarters has walk-in medical and behavioral health appointments available every weekday to support the on-site referrals described above.

#### D. Confidentiality safeguards:

All participants will receive an identification number that will be used for all forms, interviews, transcripts, and intervention materials. Forms and databases with identifying information include the demographics form and the paper consent form. The demographics form will be completed in REDCap. Consent forms will be scanned into REDCap as part of each participant's individual study record. The physical consent form will be stored in a locked filing cabinet at BHCHP that only study staff can access. Study staff will periodically hand-carry the consent forms in a locked box from the BHCHP site to the main MGH office where the files will be permanently stored in a locked filing cabinet.

Identifiable information from participants who are approached and screened but not enrolled will be saved with participant permission until recruitment ends. Once recruitment ends, we will remove any identifying information from all non-enrolled participants from our REDCap database as well as from any log sheets for tracking recruitment efforts. Identifiers in the REDCap database will be erased by using the REDCap data import tool to overwrite all identifying information. Identifiers within any additional log sheets for tracking recruitment will be manually erased. Identifiable data will be replaced with non-identifiable placeholder data.

All staff who come into contact with Human Subjects and/or data collected from Human Subjects will have received prior training about confidentiality during the course of their IRB-required Human Subjects training, which is conducted using the Collaborative IRB Training Initiative (CITI) system.

#### E. Outcomes Monitoring

Outcome monitoring will occur on a rolling basis each time a participant provides a saliva cotinine sample. Because of the low-risk nature of the study, we will not conduct a formal interim analysis of the data or define rules for early stopping of the trial.

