#### H. Data and Safety Monitoring Board (DSMB)

The DSMB will provide independent oversight of the safety monitoring of study participants. The DSMB will review the study protocol and recommend changes that may improve the protocol, as needed. Throughout the duration of the study, the DSMB will revisit the protocol to identify any emerging issues and recommend improvements and will monitor the safety of study participants by assessing social impact and adverse event reports. The DSMB may recommend modifications to the protocol, or early termination of the study, should overwhelmingly significant benefits or risks become apparent, or if the DSMB deems that the trial cannot be completed successfully.

The main objectives of the DSMB include:

- i. **Protocol review:** The DSMB will review the study protocol and data and safety monitoring plan before data collection begins. The DSMB will recommend modifications to the study protocol and safety monitoring plan as needed. The members will also review subsequent protocol changes proposed by the investigators and will recommend a timeframe for implementing protocol changes. The NCI Program Officer will be informed of any protocol changes recommended by the DSMB.
- ii. **Participant safety:** The DSMB will review unanticipated problems, adverse events, and other reportable events and formulate recommendations to continue, amend, or terminate the study based on established safety criteria.
- iii. **Study progress:** The DSMB will review screening, recruitment, and retention data to ensure that the study can be completed in a reasonable timeframe to be of significant clinical relevance.

**1) Frequency of DSMB meetings:** The DSMB will review and provide input on study procedures prior to the start of enrollment. Following the start of enrollment, the DSMB will convene at designated intervals to provide oversight of study progress and safety. The first oversight meeting will occur 6 months following the start of enrollment. Subsequent oversight meetings will occur annually, or more frequently if deemed necessary by the DSMB Chair or the study PI. Potential formats for DSMB oversight and review of study procedures could include phone conferences, video conferences, or carefully documented email exchanges at the discretion of the DSMB chair, DSMB members, and the PI [name].

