**2) DSMB reports:** The DSMB Chair will prepare a draft report of the DSMB review. The report will outline and summarize all discussions during the meeting and will clearly note recommendations and action items from the Board. The report will be reviewed by all members of the DSMB and the Principal Investigator prior to finalizing the report. The DSMB Report will be forwarded to the Project Officer. Clerical support will be provided by the MGH site as requested by the Chair of the DSMB. Following each DSMB review, the Chair shall prepare a written report to be finalized within 14 working days following the formal meeting and be sent to the PI. The report will review the 2 main aspects of the trial for which the DSMB is responsible as noted in section 2 above (see sections I.I & I.II). In addition, following each study review, the DSMB will recommend one of the following:

- i. Continuation of the trial using the current protocol and statistical plan.
- ii. Continuation of the project with modifications as outlined by the Board.
- iii. Immediate suspension of the trial for safety reasons for all participants, with a recommended plan of follow-up to minimize subject harm (requires unanimous vote).
- iv. Suspension of enrollment but continuation of assigned treatments for already-enrolled participants. Enrollment may resume once clarifications requested by the Board have been addressed and resolved (requires unanimous vote).

**3) Discussion of confidential material:** No communications, either written or oral, of the deliberations or recommendations of the DSMB will be made outside of the DSMB except as provided by written policy. Study data are strictly confidential and must not be divulged to any nonmember of the Board except as indicated by policy.

**4) Disclosure of any conflict of interest:** DSMB members will have no financial and/or scientific ties to the outcome of the study. Each DSMB member will be asked to provide financial disclosure documentation prior to the start of the member's term. Each DSMB member will also be asked to sign a confidentiality statement promising not to disclose any data.

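### Do the periodic analyses and the DSMB's stop-for-benefit wording undermine the plan's single final test at 0.05?

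*Combined protocol and SAP*

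**What the plan says.** Section IX.E, Outcomes Monitoring, states that "we will not conduct a formal interim analysis of the data or define rules for early stopping of the trial", giving the low risk of the study as the reason.

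Section IX.A, Data acquisition and monitoring, says "Analyses will occur periodically throughout the study" and that "the findings will be reported in annual progress reports to the NIH" and in the IRB's continuing review reports. It refers to a Research Strategy for the analyses themselves. That document is not among those supplied.

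Section IX.H lets the DSMB recommend "early termination of the study, should overwhelmingly significant benefits or risks become apparent". Its listed main objectives are protocol review, participant safety and study progress. On safety the DSMB is to "formulate recommendations to continue, amend, or terminate the study" by reference to safety criteria. On progress, "The DSMB will review screening, recruitment, and retention data". No efficacy item is listed.

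Section IX.H.2 gives four possible recommendations. The only halt for the whole trial is "Immediate suspension of the trial for safety reasons for all participants". The same section says "The report will be reviewed by all members of the DSMB and the Principal Investigator prior to finalizing the report". Section IX.H.3 then makes study data and the board's deliberations confidential to the board, except as written policy allows.

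Sections VI.C and VI.D plan a chi-squared test of 12-week abstinence, with 90 per arm and a two-tailed 0.05. They give no interim boundary and no division of alpha.

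**The concern.** A single test at 0.05 keeps its error rate only if earlier between-arm comparisons do not decide when the trial ends. Here one section rules out interim analysis, another provides for analyses along the way, and a third allows a stop for benefit with no boundary. In addition, the principal investigator sees the draft of a DSMB report that summarises the board's discussions.

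A reader could fear two things. The first is an inflated false-positive rate, if abstinence were compared by arm several times and the trial stopped at the first p<0.05. The second is that emerging results by arm reach an open-label team that is still recruiting and collecting an outcome with a self-report component. And if the board did recommend stopping for benefit, no standard set in advance would help to interpret the result.

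**Working it through.** **1. The plan's own figure.** Inputs from Section VI.D: p1 = 0.04, p2 = 0.175, n = 90 per arm, two-sided 0.05. The mean rate is (0.04 + 0.175)/2 = 0.1075.

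- Standard error under the null: √(2 × 0.1075 × 0.8925 / 90) = 0.04617
- Standard error under the alternative: √((0.04 × 0.96 + 0.175 × 0.825) / 90) = 0.04506
- Power: Φ((0.135 − 1.96 × 0.04617) / 0.04506) = Φ(0.987) = 83.8%

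The stated power above 80% is reproduced, and it assumes one final test. Exact enumeration of the uncorrected chi-squared test puts its type I error at 4.3% when both arms have a 4% rate, and at 5.1% when both have an assumed 10% rate.

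**2. The worst case.** The documents give no number of looks, so that number is an assumption. Suppose equally spaced looks, each tested at 0.05, with a stop at the first crossing. Exact enumeration for two, three and four looks gives 7.0%, 7.9% and 8.9% at a 4% rate, and 9.2%, 11.2% and 12.9% at a 10% rate. These figures need three things that no section provides: a by-arm abstinence look, a 0.05 threshold at that look, and a decision that follows from it.

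**3. A case nearer to the text.** The clause in Section IX.H asks for overwhelming evidence, not nominal significance. Take p<0.001 at interim looks as an illustration of such a standard, with 0.05 at the end. A crude bound for K looks is 0.05 + (K − 1) × 0.001 under normal theory, which is 0.052 for three looks. Simulation under normal theory gives about 0.051 for three looks. With the planned test, exact enumeration for two to five looks gives 4.3% at a 4% rate and 5.1% at a 10% rate, the same to one decimal as a single test.

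**4. The passages side by side.**

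- *IX.E and IX.A.* IX.E excludes a formal interim analysis. IX.A describes routine reporting to a funder and an IRB and attaches no decision to it. Pooled results, or results on which nobody acts, add nothing to the type I error.
- *IX.E and IX.H.* IX.E says that no stopping rules will be defined. IX.H says what an independent board may recommend at its discretion. A reserve power is not a rule, so both statements can hold.
- *IX.H and IX.H.2.* One names termination and the other suspension. In the safety objective, termination is tied to safety criteria, and IX.H.2 offers suspension of the whole trial for safety. The difference in wording changes no analysis.
- *IX.H.2 and IX.H.3.* Review of the draft by the principal investigator sits awkwardly with confidentiality to the board. The written policy that would settle it is not in the supplied text, so it cannot be said that a closed route is absent.

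**5. What a limit on reports would protect.** Under Section V.A.6, staff read each point-of-care result at the visit and pay the incentives arm on it, and laboratory results are sent to research staff. Under Section V.A.8, interviews are sampled by arm and abstinence status. The team can therefore follow abstinence by arm whatever the annual reports contain.

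**The case for a change.** The strongest case for a change is that Section IX.A cannot safely be read as covering accrual and safety alone. It describes recruitment and missing-data reports separately, and Section IX.F describes the annual safety summary. The sentence before the one on periodic analyses has the biostatistician receive files for the study's data analyses, which most naturally includes outcomes. De-identified files are not files masked to arm. The benefit clause has no data source, standard or matching recommendation behind it. Three small wording edits would settle all of this at no cost in participants.

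Much of this stands as description. The supplied text does not say whether the periodic analyses are by arm, and the benefit clause is unsupported elsewhere. It does not follow that the plan's result is at risk. An analyst who reads IX.E would make no confirmatory between-arm comparison before the end, and good practice would keep progress reports free of one. Deleting the benefit clause is not plainly an improvement either, because it would narrow an independent board's discretion to guard against a use that nobody has planned. What remains is the influence that knowledge of results might have on an open-label team. That comes from the design and would survive the edits.

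**Conclusion.** The concern does not call for a change. The gap in Section IX.A is one that analysts fill sensibly under IX.E. The benefit clause is a discretionary reserve power, and keeping it is a fair trade-off. The mismatch between termination and suspension is clerical.

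Followed as written, the plan keeps one final two-sided 0.05 test, with type I error of 4.3% at a 4% rate (5.1% at 10%) and power of 83.8%. A stop for benefit at p<0.001 would leave those error rates unchanged to one decimal for two to five looks.

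This rests on three assumptions: that no between-arm abstinence result is acted on at a nominal 0.05 before the end, that any stop for benefit meets a strict standard, as the clause's own wording implies, and that the Research Strategy, which was not supplied, schedules no such look. If one were scheduled and acted on at 0.05, the figures in step 2 would apply and the conclusion would change.
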